All data collectors and study investigators were blinded to the assigned treatment group. This statistical analysis plan was written before the start of any analysis. All investigators who will be running any analysis will remain blinded until initial analysis of primary outcomes is complete.

Outcome

Sweet taste preference

Our main outcome is child sweet taste preference, defined as the mean percentage sucrose score on the Monell Forced Choice taste test (1).

Statistical analysis

Analysis principles

- 1. Analysis will be by intention-to-treat. Results will be analyzed according to the group to which participants were assigned regardless of whether they got the treatment or if they followed protocol.
- 2. Data for all participants who were lost to follow-up because of death, refusal to continue with the study, or travel from study site will be included in the analysis of household and maternal baseline characteristics, if available.
- 3. Outcomes will be compared between groups using non-inferiority hypothesis testing.
- 4. Sweet taste preference scores will be compared between study groups using a non-inferiority margin of 1.64 w/v, which corresponds to an effect size of 0.2.
- 5. Analysis of treatment effect will be done using negative binomial models. The negative binomial modelling technique outputs differences between groups as ratios or percentage difference instead of mean difference. To make comparisons more efficient and easy to understand, we will convert the non-inferiority margin from the absolute value of 1.64 to a ratio (or percentage difference) by dividing 1.64 by the mean preference score of our sample. Comparisons between groups will be made using this ratio as our non-inferiority margin.
- 6. Tests will either be one-sided (main outcome comparisons) or two-sided (baseline comparisons) and at 5% level of significance, except as otherwise stated.
- 7. In reporting our results, we will report the number of observations used in the analysis wherever there are more than 10% of observations missing for a dependent or outcome variable.
- 8. In addition to the intention-to-treat analysis, we will conduct other analysis by re-running the final models in pre-specified sub-samples described below:
 - We will re-run the analysis excluding those children whose preferred sucrose solutions for series 1 and series 2 were > 2 concentrations apart.

Sample size

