The subsample size was calculated based on the primary objective: to test the hypothesis of non-inferiority of SQ-LNS regarding long term sweet taste preference as compared to no LNS. The null hypothesis is that the difference in preference score between the LNS and non-LNS group will be 1.64 % w/v or more (non-inferiority margin).

A pilot study in the study area showed the preferred percentage sucrose solution score to be 15.7 ± 8.2 %. Assuming a standard deviation of 8.2 percent sucrose and a pre-determined non-inferiority margin of 1.64 percent sucrose w/v (an effect size of 0.2), a sample size of 620 was estimated to provide the trial with 80% power and 95% confidence to discard the inferiority null hypothesis. Adjusting for 15% attrition rate (including child deaths, loss to follow-up, refusals) brings the total sample size to 713 (356 participants per group).

Study flowchart

A participant flow diagram will be prepared in accordance with the CONSORT 2010 guidelines. The figure (Figure 1 below) will include the numbers and reasons for permanent loss to follow up between the start of the main trial and end of the follow-up study.

Data cleaning

Data cleaning for this follow-up study was done alongside data collection. Range checks were built into direct data entry by enumerators. SAS syntax were written and run weekly to generate a list of queries on plausible but extreme values or inconsistent responses, which were then examined and resolved with the help of the field worker. The corrections/ changes were then recorded in a "data cleaning excel sheet" which was used to generate additional syntax and a corrected data set.

Outliers

Data will be visually examined by means of histograms (for individual continuous variables) and scatter plots (of related variables) to check for outliers after which they will be investigated. Outliers which are clearly implausible or impossible will be corrected if possible or recoded to missing where correction is not possible. Those that are plausible or possible will be kept in the dataset. During analysis, we will transform variables with outliers, and if needed, we will conduct sensitivity analysis by running the models with and without these outliers to examine if these outliers have undue influence on the results.

Software for analysis

All analyses will be done using SAS version 9.4 (SAS Inst. Cary, NC, USA).

Baseline characteristics of participants and baseline comparisons

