Baseline characteristics will be compared between groups using ANOVA for continuous variables or a chisquare test for categorical variables. If there are dropouts (selected for the subsample but who were not
tested for various reasons), we will compare baseline characteristics between participants who will be
included in the analysis and the dropouts. Baseline characteristics will be selected household and
maternal characteristics at baseline, that is, all available values for these selected variables at the time of
maternal enrolment into the main study, prior to first intake of study supplement. Child age will however
be the age of child at the time of sweet taste preference testing. In analyzing baseline characteristics:

[figure not shown]
- Means and SE (or SD) or medians and 25th and 75th percentiles will be used to describe continuous data.
- 2. Frequencies and percentages will be used to summarize categorical data. We will calculate percentages based on the number of participants for whom data are available.
- 3. Where data for certain participants are missing (>10 %), the number of participants included in the analysis will be indicated.

Analysis of the impact of the intervention

Negative binomial models will be used to test the null hypothesis of inferiority between the two groups. We will first run the models without covariates, then run them again controlling for pre-specified covariates. Only covariates significantly associated with the outcome at 10% level of significance in bivariate analysis will be included in the final adjusted analysis. Results will be presented as the difference

in means between the two groups. The 95% confidence interval will be reported. Results will be interpreted as follows (and graphed below):

- 1. If the entire 95% CI is below the non-inferiority margin, we conclude that **non-inferiority** has been established
- 2. If the lower level of the 95% CI is greater than the non-inferiority margin, we conclude that the treatment group is **inferior** (worse in sweet taste/ have higher preference for sweet taste) to the control group.
- 3. If the upper level of the 95% CI is greater than the non-inferiority margin and the lower level is less than the non-inferiority margin, we conclude that the result is **inconclusive**.

Difference in preferred percent sucrose score (LNS group vs. non-LNS group)

Potential covariates

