Independent of the intervention, child sweet taste preference could be influenced by a variety of household, maternal, and infant factors. Each pre-specified covariate (listed below), will be examined for completeness of data, and a decision will be made for the exclusion of any covariate with a high proportion of missing data. Potential covariates that will be examined include:

- Maternal years of formal education
- Maternal estimated pre-pregnancy BMI
- Maternal marital status
- Maternal age
- Parity
- Child age at testing
- Child sex
- Household Assets Index (baseline)
- Household food insecurity index (baseline)
- Distance to market
- Ethnicity

Data transformations

We will examine the residuals of continuous outcome variables to assess if they conform to the normal distribution using the Shapiro-Wilk test. Shapiro-Wilk statistic values >0.97 will be considered acceptable. Any continuous outcome whose residuals are not normally distributed will be transformed appropriately.

Figures and Tables

The following figures and tables are only drafts. They will be examined and final decisions on presentation of information will be made by the manuscript writing group later.

Figures:

Figure 1 will be the study flow chart (shown below) and figure 2 will be the non-inferiority graph shown above.

Figure 1: Study Flow chart

Tables

Variable ³	LNS	No LNS
Number of participants		
Maternal age (y)		
Maternal education (y)		
Married or cohabiting (%)		
Maternal pre-pregnancy BMI (kg/m²)		
Parity (#)		
Ethnicity (%)		
Child male sex (%)		
Child age at follow-up (mo)		
Household Assets Score (#)		
Household Food Insecurity Score (#)		
Distance to market (#)		

²LNS=lipid-based nutrient supplement; Non-LNS = exposure to IFA/MMN but no LNS

³Data will be presented as mean ± SD or Median (Q1, Q3) depending on the distribution

Variable ²	LNS	Non-LNS	P-Value ³
Total time required			
Series 1			
Series 2			
Number of pairs (trials) required to reach criterion			
Series 1			
Series 2			
Both series			
Agreement between series 1 and 2 [n (%)]			
Preferred same solution			
Preferred one concentration higher/lower			
Preferred two concentrations higher/lower			
Preferred more than two concentrations higher/lower			

¹LNS=lipid-based nutrient supplement; Non-LNS = exposure to IFA/MMN but no LNS

²Data will be presented as mean ± SD or Median (Q1, Q3) depending on the distribution

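### The SAP does not say whether the unadjusted or the outcome-screened adjusted model decides non-inferiority, and it leaves the adjusted model's covariates to be chosen from the data

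*SAP*

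**What the plan says.** Under 'Analysis of the impact of the intervention' the SAP plans two fits for its one hypothesis: "We will first run the models without covariates, then run them again controlling for pre-specified covariates". The next sentence narrows the covariates by their relation to the outcome: "Only covariates significantly associated with the outcome at 10% level of significance in bivariate analysis will be included in the final adjusted analysis".

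The interpretation rule follows: "If the entire 95% CI is below the non-inferiority margin, we conclude that" non-inferiority is established. Two further rules cover inferiority and an inconclusive result. None of the three says which fit supplies the interval. Draft Table 3 has an unadjusted and an adjusted row, each with a difference and a 95% CI, and ranks neither.

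'Potential covariates' introduces its 11 candidates with "Potential covariates that will be examined include" and adds a second filter, under which "a decision will be made for the exclusion of any covariate with a high proportion of missing data". It gives no threshold, and no rule for children who lack a value for a covariate that is kept.

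On the error rate, 'Analysis principles' item 6 says "Tests will either be one-sided (main outcome comparisons) or two-sided (baseline comparisons) and at 5% level of significance, except as otherwise stated", while the impact section says "The 95% confidence interval will be reported" and decides on that interval.

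**The concern.** The trial has one hypothesis, so the SAP should fix which interval answers it. Here two intervals exist, they will not be identical, and nothing ranks them. If one lies wholly below the margin and the other crosses it, the SAP supports both a claim of non-inferiority and an inconclusive result. The choice would then be made with both results in view.

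A second weakness is that the adjusted model is not known in advance. Its covariates depend on p-values against the outcome and on an undefined judgement about missing data. If children with missing covariate values drop out of the adjusted fit, the two models would also describe different children.

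At stake are the error rate of a non-inferiority claim, an unambiguous verdict, and the precision that adjustment can bring.

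**Working it through.** **Inputs from the SAP.** Margin 1.64 and SD 8.2 ("pre-determined non-inferiority margin of 1.64 percent sucrose w/v (an effect size of 0.2"); total 620, so 310 per group; power 80%; 11 candidate covariates; screening at p < 0.10; one-sided 5% ('Analysis principles') or a 95% CI (impact section).

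**Assumed.** The share R² of outcome variance explained by the covariates is not in the SAP. The main range is 0.05 to 0.10, and the simulation below covers 0 to 0.30. A linear model on the sucrose scale stands in for the negative binomial.

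**1. The SAP's own figure.** n per group = 2 × (z₁₋α + z₀.₈₀)² × (8.2/1.64)².
- One-sided 5%: 2 × (1.645 + 0.842)² × 25 ≈ 309.1, so 310 per group and 620 in total. This matches.
- One-sided 2.5%: 2 × (1.960 + 0.842)² × 25 ≈ 392.4, so 393 per group and 786 in total. This does not match.

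The sample size therefore rests on one-sided 5%, while the decision rule, read as a two-sided interval, works at 2.5%. Both are shown below.

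**2. Error if either model may declare non-inferiority.** With the true difference at the margin, the two test statistics are approximately bivariate normal with correlation √(1 − R²). Then P(either) = 2α − P(both).

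| R² | Correlation | α = 5%: both / either | α = 2.5%: both / either |
|---|---|---|---|
| 0.05 | 0.975 | 4.08% / 5.9% | 1.98% / 3.0% |
| 0.10 | 0.949 | 3.69% / 6.3% | 1.76% / 3.2% |

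**3. Simulation with the p < 0.10 screen.** 20,000 runs per scenario, 310 per group, 11 independent candidates, R² spread over 8 of them, true difference 1.64.

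| R² | Either model, α = 5% | Either model, α = 2.5% |
|---|---|---|
| 0 | 5.4% | 2.8% |
| 0.02 | 5.6% | 2.7% |
| 0.05 | 6.3% | 3.2% |
| 0.10 | 6.3% | 3.5% |
| 0.20 | 7.1% | 3.7% |
| 0.30 | 7.3% | 3.8% |

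Single models over the same range:
- Screened adjusted model alone: 5.0–5.5% (α = 5%) or 2.4–2.7% (α = 2.5%).
- Model with all 11 covariates fixed: 4.7–5.1% or 2.3–2.6%.

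Most of the excess therefore comes from having two unranked analyses, not from the screen.

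**4. What the screen does.** With no real associations, 11 × 0.10 = 1.1 covariates enter by chance (simulated 1.10). At R² = 0.05 the simulation keeps 5.29 covariates on average. About 3 × 0.10 = 0.3 of these are noise, so about 5.0 of the 8 real predictors are kept and about 3 are lost.

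**5. Opposite verdicts when the true difference is 0.** The standard error is 8.2 × √(2/310) = 0.6586, so the margin lies 1.64/0.6586 = 2.49 standard errors away (unadjusted) or 2.49/√(1 − R²) (adjusted). The chance that exactly one model succeeds is P(unadjusted) + P(adjusted) − 2 × P(both):
- α = 5%: 5.1% at R² = 0.05 and 7.3% at R² = 0.10.
- α = 2.5%: 6.4% and 9.3%.

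**6. Power of a fixed adjusted set.** Power = Φ(2.49/√(1 − R²) − z₁₋α).

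| R² | α = 5% | α = 2.5% |
|---|---|---|
| 0 (unadjusted) | 80% | 70% |
| 0.05 | 82% | 72% |
| 0.10 | 84% | 75% |

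**The case against.** The strongest reply is that under the SAP's own decision rule the error does not pass 5%. A two-sided 95% interval allows 2.5% per analysis. Even two fully independent tests would give 1 − 0.975² = 4.9%, and the two models here are highly correlated. This stands. A reader might infer that the claim's error rate exceeds 5%, but that holds only if the decision is taken at one-sided 5%, and the SAP supports both readings. On the 95% interval the excess is over 2.5%.

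A second reply is that screening does little harm to the error rate. It uses the association of covariates with the outcome and not the treatment effect, the candidate list is fixed, the SAP was written before any analysis, and analysts stay blinded until the initial primary analysis is complete. This also stands: the screened model alone is near nominal. A reader might take both analyses to be shaped by the data, but the unadjusted model has no covariates to select.

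A third reply is that the SAP nowhere says that success on either model suffices, and that its references to a final adjusted analysis and to final models point towards the adjusted one. The first part is right: this is an omission, not a stated either-or rule. The second part does not settle the matter, because those terms name a modelling step and the decision rule does not refer to them. Blinding does not settle it either, since it does not say which interval counts when the two differ.

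**Conclusion.** The point holds, with modest size. The SAP does not designate the deciding model and has no rule for disagreement. If either model could carry the claim, at an assumed R² of 0.05 to 0.10 the error would be about 0.9 to 1.3 points above a nominal 5%, or about 0.5 to 0.7 points above a nominal 2.5%. The more practical consequence is that, with a truly harmless product, roughly one trial in 11 to 20 would end with two models pointing to different conclusions.

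The documents do not support the stronger readings that the screen by itself inflates the error materially, or that the SAP permits a claim on whichever interval succeeds. The case against screening is different: with 11 candidates and about 620 children it is not needed, and it leaves to chance how much of a small power gain (2 to 5 points) is realised.

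The figures rest on an assumed R², independent covariates in the simulation, a linear approximation to the negative binomial, and 310 children per group.

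**What to change.** - Name one deciding analysis: the negative binomial model adjusted for all 11 covariates listed under 'Potential covariates', with no screening on the outcome. Say that the interpretation rules apply to its interval.
- Replace the undefined exclusion for missing data with one stated method for missing baseline covariate values, for example simple imputation, so that every tested child stays in the model.
- Label the unadjusted model supportive, in the text and in Table 3, and say that a differing result does not change the conclusion.

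In the simulation this brings the error back to about nominal (4.7–5.1% at 5%; 2.3–2.6% at 2.5%). The sample size of 620 is unchanged. The cost is SAP wording and one degree of freedom per covariate (more for ethnicity if it has several categories), out of about 620.

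### The conclusion rule tests at one-sided 2.5%, but the test level and the sample size are set at one-sided 5%, so power under the rule is about 70% rather than 80%

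*SAP*

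**What the plan says.** Three parts of the SAP bear on the level at which non-inferiority is judged.

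- **Analysis principles, item 6:** "Tests will either be one-sided (main outcome comparisons) or two-sided (baseline comparisons) and at 5% level of significance, except as otherwise stated". The main outcome is therefore tested one-sided at 5% by default.
- **Sample size:** "Assuming a standard deviation of 8.2 percent sucrose and a pre-determined non-inferiority margin of 1.64 percent sucrose w/v (an effect size of 0.2"), the section says that "a sample size of 620 was estimated to provide the trial with 80% power and 95% confidence to discard the inferiority null hypothesis". Attrition then raises the total to 713, or 356 per group.
- **Analysis of the impact of the intervention:** "The 95% confidence interval will be reported". Rule 1 concludes non-inferiority "If the entire 95% CI is below the non-inferiority margin". Rule 3 gives an inconclusive result "If the upper level of the 95% CI is greater than the non-inferiority margin and the lower level is less than the non-inferiority margin". Rule 2 concludes inferiority when the lower limit exceeds the margin.

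Draft Table 3 also presents a 95% CI and has no p-value column. The SAP mentions neither a 90% interval nor a one-sided confidence bound.

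**The concern.** Requiring the upper limit of a two-sided 95% CI to lie below the margin is the same as a one-sided test at 2.5%. Item 6 calls for one-sided 5%. The two criteria can classify the same data differently: an estimate may reject the inferiority null at the item 6 level and still be inconclusive under rule 3.

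This affects the study's only primary conclusion. If the SAP does not say which criterion governs, the choice could be made after the result is known. The stated power is also at issue. If 620 was derived at one-sided 5%, the 80% does not apply to the rule that will produce the conclusion, and a truly neutral supplement would be left unresolved more often than the plan says.

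**Working it through.** **Inputs**

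- SD 8.2 and margin 1.64 % w/v, a ratio of 0.2 (Sample size)
- 620 evaluable, 80% power; 713 after attrition, 356 per group, so 1:1 allocation (Sample size)
- One-sided 5% (Analysis principles, item 6)
- Two-sided 95% CI (Analysis of the impact of the intervention, rules 1 to 3)
- True difference 0: not stated in the SAP, but it is the value that reproduces 620

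**Step 1. Reproduce the plan's figure**

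n per group = 2 × [(z(1−α) + z(0.80)) × SD / margin]², with SD / margin = 8.2 / 1.64 = 5.

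- One-sided 5%: 2 × [(1.645 + 0.842) × 5]² = 309.1, so 310 per group, **620 in total**. This matches exactly.
- One-sided 2.5%: 2 × [(1.960 + 0.842) × 5]² = 392.4, so 393 per group, **786 in total**. This does not match.

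The subsample was therefore sized for a one-sided 5% test.

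**Step 2. Power under each criterion**

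SE = 8.2 × √(2/n); power = Φ(1.64/SE − z). At 310 per group, SE = 8.2 × √(2/310) = 0.6586 and 1.64/0.6586 = 2.490.

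- One-sided 5%: Φ(2.490 − 1.645) = 80.1%
- 95% CI rule: Φ(2.490 − 1.960) = 70.2%

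The noncentral t distribution gives 80.0% and 70.1%.

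| Evaluable per group | One-sided 5% | 95% CI rule |
|---|---|---|
| 303 (713 × 0.85 = 606) | 79.3% | 69.2% |
| 310 (planned 620) | 80.1% | 70.2% |
| 356 (no attrition) | 84.7% | 76.1% |

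No planned sample size gives 80% power under the CI rule.

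**Step 3. Results on which the criteria disagree (310 per group)**

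The largest observed difference (LNS minus non-LNS) that passes is:

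- One-sided 5%: 1.64 − 1.645 × 0.6586 = +0.557
- 95% CI rule: 1.64 − 1.960 × 0.6586 = +0.349

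An estimate between about +0.35 and +0.56 % w/v passes under item 6 and is inconclusive under rule 3. With a true difference of 0, this happens in 80.1% − 70.2% = 9.9% of trials.

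**The case against.** The strongest counter-argument is the closing clause of item 6, which lets other text override the default level. The interpretation rules are specific to the main outcome and are the only place where a conclusion is defined, and Table 3 is built around the 95% CI. On that reading there is one governing rule. This is a fair reading and weakens the claim of two competing rules. But the rules do not announce themselves as an exception. If they are one, item 6's explicit one-sided level for the main outcome governs nothing, and the stated power is still wrong for the rule that applies.

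Three further points stand as limits.

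- **The error is conservative.** The CI rule holds the one-sided type I error at 2.5%, so false claims of non-inferiority are not inflated. In the disputed band the rule returns inconclusive, not inferior.
- **The 70% rests on assumptions.** It needs a true difference of 0, 310 evaluable per group and a normal comparison of means. The planned analysis is a negative binomial model with the margin converted to a ratio. A rough check on the log scale, taking the pilot mean of 15.7 and SD of 8.2 and 310 per group, has a log margin of ln(1 + 1.64/15.7) = 0.0993 and SE of (8.2/15.7) × √(2/310) = 0.0420. Power is then about 77% at one-sided 5% and 66% under the CI rule. The model changes the figures but does not remove the gap.
- **Data collection ended in December 2016.** The 786 is therefore informative only.

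Reading the Sample size section's confidence level as a one-sided 95% bound fits that section, but not rules 2 and 3, which need both limits.

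**Conclusion.** The concern holds. The sample size reproduces only at one-sided 5%, while the conclusion rule operates at one-sided 2.5%. On the plan's own sizing basis (SD 8.2, margin 1.64, 1:1, true difference 0, normal means, 310 per group) the rule has 70.2% power, not 80%. A truly neutral supplement would fail to show non-inferiority about 30% of the time rather than 20%. The shortfall persists over the range of planned numbers, from 69.2% at 303 per group to 76.1% at 356. Whether one reads the SAP as having two criteria or one, the stated power and the conclusion rule do not agree. Because this governs the primary conclusion, it must be settled before unblinding.

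**What to change.** State one level and use it in item 6, in Sample size, in interpretation rules 1 to 3 and in Figure 2. Either option is coherent.

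1. **One-sided 5%.** Base rules 1 to 3 and Figure 2 on the two-sided 90% CI, whose upper limit is the one-sided 95% bound. Show the 95% CI as descriptive. This agrees with item 6 and with 80% power at 620. It loosens the only explicit conclusion rule after data collection, so the change should be dated and documented as made while the analysts are still blinded.
2. **One-sided 2.5%.** Keep the 95% CI in rules 1 to 3, change item 6 to one-sided 2.5% for the main outcome, and restate the power for 620 as about 70%, with the assumption of no true difference made explicit.

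Both are changes of SAP wording only and need no new data. The price of the second is a less favourable power statement.
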